16.1 Study Information

16.1.1 Protocol and protocol amendments

The following documents are included:

- Final protocol, dated 29 Jan 2016.

CLINICAL STUDY PROTOCOL

Protocol No. TEN-01-303

An Open Label Long-Term Safety Study of Tenapanor for the Treatment of Constipation-Predominant Irritable Bowel Syndrome (IBS-C)

29 January 2016
Edition No. 1

SPONSOR:

Ardelyx, Inc.
[name]
[name]

Confidentiality Statement

This document and the information contained herein or attached hereto ("Confidential Material") are confidential and proprietary to Ardelyx, Inc. This Confidential Material should be viewed only by those individuals or companies that have been given prior authorization to do so by Ardelyx, Inc. ("Authorized Users"). This Confidential Material should not be made available in any form to any person or company, other than the Authorized Users and their respective employees or associates on a need-to-know basis, without the prior written consent from Ardelyx, Inc.

PROTOCOL SUMMARY

Study Title	An Open Label Long-Term Safety Study of Tenapanor for the Treatment of Constipation-Predominant Irritable Bowel Syndrome (IBS-C)
Sponsor	Ardelyx, Inc.
Study Phase	3
Treatment Groups	Single treatment group; approximately 300 subjects total
No. of Sites	Approximately 50-60
Dose Form and Frequency	Tablet(s) Twice daily (BID)
Doses	Tenapanor 50 mg BID (total daily dose 100 mg)
Methodology	This is an open label study to evaluate the safety of tenapanor 50 mg BID in subjects with IBS-C (Rome III criteria). Subjects who have completed either the TEN-01-301 (16 weeks) or TEN-01-302 (26 weeks) studies may be enrolled. Subjects will take tenapanor for up to 52 weeks total based on previous protocol and this study.
Duration	For each subject, the entire exposure to tenapanor will last for a total of approximately 52 to 55 weeks; including completion of either the TEN-01-301 or TEN-01-302 studies. For subjects completing studies TEN-01-301 or TEN-01-302, TEN-01-303 treatment duration will be 39 and 26 weeks, respectively.

Treatment Period	During the treatment period of up to 39-weeks subjects will return for study visits approximately every 13 weeks (see schedule of events). Subjects will undergo safety assessments at these visits, which may include a physical exam, ECG, vital signs, and clinical labs. Adverse events and concomitant medications will be recorded. Medication compliance will be monitored and the subjects will be given additional study drug as appropriate.
Inclusion/Exclusion Criteria	
Inclusion Criteria
 
Subjects meeting all of the following inclusion criteria will be eligible for enrollment:
 
1. Subjects completed all 16 weeks of TEN-01-301 or all 26 weeks of TEN-01-302.2. In the opinion of the investigator, the subject demonstrated adequate compliance with the study procedures during either the TEN-01-301 or TEN-01-302 studies preceding this long term safety study.3. Females must be of non-childbearing potential; either postmenopausal for at least 12 months as confirmed by follicle-stimulating hormone test (if < 60 years old), or surgically sterile (e.g., tubal ligation, hysterectomy, bilateral oophorectomy with appropriate documentation) as determined in either TEN-01-301 or TEN-01-302 studies. If of child-bearing potential, must have negative pregnancy test at last visit for TEN-01-301 or TEN-01-302 and confirm the use of one of the following appropriate means of contraception:
• Oral birth control pills administered for at least one monthly cycle prior to study drug administration,• Contraceptive patch worn for at least one monthly cycle prior to study drug administration,• Progesterone implants,• IUDs,• Abstinence from intercourse for two weeks prior to the study drug administration, throughout the study, or• Double barrier method,• Sterilization of one or both partner(s).4. Males must agree to use an appropriate method of barrier contraception (e.g., latex condom with a spermicidal agent) or have documented surgical sterilization

	
5. The subject has signed the informed consent and is willing to comply with all trial visits and assessments
 
Exclusion Criteria
 
Subjects meeting one or more of the following exclusion criteria are not to be enrolled in the study:
 
1. The subject has been withdrawn or discontinued prematurely from either TEN-01-301 or TEN-01-3022. The subject reports using any prohibited medication and is not willing to abide by the restrictions for intake3. Pregnant or lactating women.4. If, in the opinion of the Investigator the subject is unable or unwilling to fulfill the requirements of the protocol or has a condition, which would render the results uninterpretable.
Statistical Considerations	
Summary tabulations will be presented that will display descriptive statistics at each visit for each treatment cohort and for all subjects in the safety analysis set. For continuous variables, descriptive statistics will include the number of subjects, mean, standard deviation, minimum, median, and maximum values. For categorical variables, descriptive statistics will include the number and percent of subjects in each category.
 
All subjects who receive at least one dose of study drug will be included in all analyses of safety.
 
Safety analyses will include summaries for treatment emergent adverse events, clinical laboratory tests, vital signs, 12-lead ECGs, and physical exams. Study drug exposure, compliance and concomitant medications will also be summarized.

TABLE OF CONTENTS

PROTOCOL SUMMARY	2
TABLE OF CONTENTS	5
1. LIST OF ABBREVIATIONS.....	7
2. INTRODUCTION AND STUDY RATIONALE	9
2.1. Scientific Background	9
2.2. Description of Investigational Drug	9
3. STUDY OBJECTIVES	10
3.1. Primary Objective.....	10
4. INVESTIGATIONAL PLAN.....	10
5. STUDY POPULATION	11
5.1. General Considerations	11
5.2. Inclusion Criteria	11
5.3. Exclusion Criteria.....	11
5.4. Rescue Medication	12
5.5. Prohibited Concurrent Medications.....	12
5.6. Removal of Subjects from Therapy or Assessment	12
6. TREATMENTS	13
6.1. Identity of Investigational Product	13
6.2. Packaging, Storage, and Labeling	13
6.3. Treatments to be Administered	13
6.4. Randomization and Blinding.....	13
7. SCHEDULE OF ASSESSMENTS.....	14
8. STUDY EVALUATIONS.....	15
8.1. Evaluations and procedures at Visit 1 (Day 1).....	15
8.2. Safety Assessments	16
8.3. Total Blood Volume Required for Study	17
8.4. Data Quality Assurance	17
9. ADVERSE EVENTS.....	18

1. LIST OF ABBREVIATIONS

AE	Adverse event
ALT	Alanine aminotransaminase
AST	Aspartate aminotransaminase
BM	Bowel movement
BMI	Body mass index
BSFS	Bristol stool form scale
BUN	Blood urea nitrogen
CIC	Chronic idiopathic constipation
CKD	Chronic kidney disease
CO ₂	Carbon dioxide
CRC	Child resistant closure
CRF	Case report form;
CRO	Contract research organization
CSBM	Complete spontaneous bowel movement
ECG	Electrocardiogram
eCRF	Electronic case report form
EDC	Electronic data capture
ESRD	End-stage renal disease
FDA	Food and drug administration
FSH	Follicle-stimulating hormone
GCP	Good clinical practice
GI	Gastrointestinal
H ⁺	Hydrogen
HDPE	High density polyethylene
IB	Investigator's brochure
IBS	Irritable bowel syndrome
IBS-C	Constipation predominant irritable bowel syndrome
IBS-D	Diarrhea predominant irritable bowel syndrome
IBS-M	Mixed irritable bowel syndrome (constipation and diarrhea)
IBS-QOL	Irritable bowel syndrome quality of life questionnaire
ICF	Informed consent form
ICH	International conference on harmonization
IEC	Independent ethics committee

IRB	Institutional review board
ITT	Intent to treat
IVRS	Interactive voice response system
IWRS	Interactive web response system
LDH	Lactate dehydrogenase
MCH	Mean corpuscular hemoglobin
MCHC	Mean corpuscular hemoglobin concentration
MCV	Mean corpuscular volume
MedDRA	Medical Dictionary for Drug Regulatory Activities
Na ⁺	Water/sodium
NHE ₃	Sodium-hydrogen antiporter 3
OBD	Opioid bowel dysfunction
QA	Quality assurance
RBC	Red blood cell
SAE	Serious adverse event
SAP	Statistical analysis plan
SBM	Spontaneous bowel movement
SOP	Standard operating procedure
TEAE	Treatment emergent adverse event
WBC	White blood cell count
WHO	World health organization

2. INTRODUCTION AND STUDY RATIONALE

A major function of the gastrointestinal (GI) tract is to maintain intestinal water/sodium (Na⁺) homeostasis through a delicate balance of secretory and absorption mechanisms. The Na⁺/hydrogen (H⁺) antiporter NHE3 plays a dominant role in the Na⁺ re-uptake process. Tenapanor (also known as RDX5791 and AZD1722) is a GI-acting NHE3 inhibitor. Tenapanor is a minimally systemic, small molecule under investigation for the treatment of constipation-related diseases such as chronic idiopathic constipation (CIC), constipation predominant irritable bowel syndrome (IBS-C), and opioid bowel dysfunction (OBD). The proposed mechanism of action of tenapanor is to reduce Na⁺ re-uptake. This decrease in Na⁺ uptake increases the net fluid volume in the GI tract. Restoration of normal luminal fluid content facilitates intestinal transit and stimulates motility.

This open label long-term safety study will evaluate the safety of tenapanor in subjects with constipation predominant IBS (IBS-C) who have completed either study TEN-01-301 (16 weeks) or TEN-01-302 (26 weeks). Subjects who qualify will receive tenapanor 50 mg BID for up to 52 weeks total based on previous protocols and this study. For subjects completing studies TEN-01-301 or TEN-01-302, treatment duration will be 39 and 26 weeks, respectively.

2.1. Scientific Background

2.1.1 Overview of IBS

Irritable bowel syndrome (IBS) is the most common disorder seen by gastroenterologists and is characterized by abdominal pain with associated alterations in bowel function. These changes in bowel patterns may manifest as diarrhea, constipation or an alternation between the two. As there are no pathognomonic, laboratory, endoscopic or radiographic abnormalities found in association with IBS it is considered a functional gastrointestinal (GI) disorder. The chronic nature of the multiple symptoms of IBS, combined with the lack of effective treatments, leads to significant health care resources being used by IBS subjects and impairment of subjects' well-being and functional ability. For research and regulatory purposes, the diagnosis of IBS has been described by the Rome III criteria as summarized in Appendix A.

2.2. Description of Investigational Drug

Tenapanor is chemically described as: (S)-N,N'-(10,17-dioxo-3,6,21,24-tetraoxa-9,11,16,18-tetraazahexacosane-1,26-diyl)bis(3-((S)-6,8-dichloro-2-methyl-1,2,3,4-tetrahydroisoquinolin-4-yl) benzenesulfonamide) dihydrochloride. Its empirical formula is C₅₀H₆₈Cl₁₆N₈O₁₀S₂.

Tenapanor (as the dihydrochloride salt) drug product will be supplied as white to off-white oval biconvex film-coated tablets with the following excipients:

Tenapanor will be supplied at a dosage strength of 50 mg. Tablets are packaged in an opaque white HDPE (high-density polyethylene) bottle (66/bottle) with a white polypropylene CRC closure and induction seal plus

desiccants. Tablets of tenapanor should be stored in the original packaging between 2°C and 30°C. Temperature excursions are allowed from -30°C to 50°C excursions for a maximum of 1 week.

3. STUDY OBJECTIVES

3.1. Primary Objective

The primary objective of this study is to assess the safety of tenapanor 50 mg for the treatment of IBS-C when administered twice daily (BID) for up to 52 weeks.

4. INVESTIGATIONAL PLAN

This is an open label long-term safety study of tenapanor in subjects with IBS-C. Subjects who have completed either study TEN-01-301 or TEN-01-302 will be eligible to enroll in this study.

During the open label treatment period, subjects will return for study visits approximately every 13 weeks (see schedule of events). Subjects will undergo safety assessments at these visits, which may include a physical exam, ECG, vital signs, and clinical labs. Adverse events and concomitant medications will be recorded. Medication compliance will be monitored and the subjects will be given additional study drug as appropriate.

5. STUDY POPULATION

5.1. General Considerations

Approximately three-hundred (300) subjects who have completed TEN-01-301 or TEN-01-302 and meet all of the inclusion criteria, and none of the exclusion criteria will be enrolled into the study at approximately 50 to 60 US clinical centers.

5.2. Inclusion Criteria

Subjects meeting all of the following inclusion criteria will be eligible for enrollment:

1. Subjects completed all 16 weeks of TEN-01-301 or all 26 weeks of TEN-01-302.
2. In the opinion of the investigator, the subject demonstrated adequate compliance with the study procedures during either TEN-01-301 or TEN-01-302 studies preceding this long term safety study.
3. Females must be of non-childbearing potential; either postmenopausal for at least 12 months as confirmed by follicle-stimulating hormone test (if < 60 years old), or surgically sterile (e.g., tubal ligation, hysterectomy, bilateral oophorectomy with appropriate documentation) as determined in either TEN-01-301 or TEN-01-302 studies. If of child-bearing potential, must have negative pregnancy test at last visit for TEN-01-301 or TEN-01-302 and confirm the use of one of the following appropriate means of contraception:
 - Oral birth control pills administered for at least one monthly cycle prior to study drug administration,
 - Contraceptive patch worn for at least one monthly cycle prior to study drug administration,
 - Progesterone implants,
 - IUDs,
 - Abstinence from intercourse for two weeks prior to the study drug administration, throughout the study, or
 - Double barrier method,
 - Sterilization of one or both partner(s).
4. Males must agree to use an appropriate method of barrier contraception (e.g., latex condom with a spermicidal agent) or have documented surgical sterilization
5. The subject has signed the informed consent and is willing to comply with all trial visits and assessments

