5.3. Exclusion Criteria

Subjects meeting one or more of the following exclusion criteria are not to be enrolled in the study:

1. The subject has been withdrawn or discontinued prematurely from either TEN-01-301 or TEN-01-302

2. The subject reports using any prohibited medication and is not willing to abide by the restrictions for intake
3. Pregnant or lactating women.
4. If, in the opinion of the Investigator the subject is unable or unwilling to fulfill the requirements of the protocol or has a condition, which would render the results uninterpretable..

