2.2.3 Duration of Study

For each subject, the entire study will last for a total of approximately 52 to 55 weeks; including completion of either the TEN-01-301 or TEN-01-302 studies. For subjects completing studies TEN-01-301 or TEN-01-302, TEN-01-303 treatment duration will be 39 and 26 weeks, respectively. The study flow chart, including all procedures to be performed during the study is presented below.

SCHEDULE OF ASSESSMENTS FOR THE STUDY

The study flow chart, including all procedures to be performed during the study is presented below. Prior to engaging in any study procedure, each subject must sign and date an informed consent form. In addition, a telephone contact will take place as footnoted below to find out if any treatment related problems have occurred. Additional telephone calls to the subjects for treatment follow-ups of AEs will be made as needed.

Evaluation	Enroll ^a	Treatment Period		
		1	2	3 ^b
Site Visit ^h	1	2	3 ^b	4/ET ^c
Study Week	1	13±2	26±2	39±2
Informed Consent ^a	X			
Inclusion/Exclusion	X			
Concurrent Medications		X	X ^{b#}	X
Physical Exam			X ^b	X
Vital Signs ^d		X	X ^{b#}	X
Clinical Laboratory Tests ^f			X ^b	X
Urine Pregnancy test ^{fg}		X	X ^{b#}	X
Urinalysis ^f			X ^b	X
12-lead ECG			X ^b	X
Drug Dispensed/returned	D	D/R	D [#] /R ^{b#}	R
Adverse Event Assessments		X	X ^{b#}	X

^a The Informed Consent Form (ICF) must be signed before any protocol procedures are performed.

^b This is the final visit for subjects who enrolled from Protocol TEN-01-302 and only procedures with this footnote are performed. Procedures for subjects enrolled from Protocol TEN-01-301 are marked with a #.

^c This is the final visit for subjects who enrolled from Protocol TEN-01-301.

^d Vital signs include systolic and diastolic blood pressure (seated), heart rate, respiratory rate, temperature and body weight.

^e When a subject discontinues early, procedures performed at Visit 4 should be performed at the subject's last visit.

^f Laboratory assessments are detailed in Appendix A of the protocol.

^g If the urine pregnancy test is positive, it will be confirmed with a serum pregnancy test.

^h Telephone calls will be made to subjects monthly during the two months prior to a site visit to ascertain if there have been any treatment related problems (Weeks 5±1, 9±1, 17±1, 22±1, for subjects from TEN-01-301 and TEN-01-302 and for subjects from TEN-01-301 also Weeks 30±1 and 35±1).

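### If Visit 1 falls after the last parent-study visit, drug can be dispensed with no pregnancy test at entry, because no rollover interval is set

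*Protocol*

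**What the plan says.** Protocol Section 5.2, criterion 3, sets two conditions for women of child-bearing potential: the woman "must have negative pregnancy test at last visit for TEN-01-301 or TEN-01-302", and she confirms that she uses one of the listed contraceptive methods. Section 5.3 separately excludes "Pregnant or lactating women".

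On timing, Section 4 asks only for completion of a parent study: "Subjects who have completed either study TEN-01-301 or TEN-01-302 will be eligible to enroll in this study". Section 8 counts later visits from the day of enrolment.

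Section 8.1 lists three items for Visit 1: consent, the eligibility criteria and dispensing. Section 8.2.1.5 places urine pregnancy tests at Visits 2, 3 and 4, with serum confirmation of a positive result. The flow charts in Protocol Section 7 and SAP Section 2.2.3 agree: neither has a pregnancy test in the Visit 1 column. Section 8.1.1 has telephone contacts at Weeks 5 ± 1 and 9 ± 1, which cover medication changes and adverse events.

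On duration, the Protocol Summary says that "TEN-01-303 treatment duration will be 39 and 26 weeks, respectively" for subjects from TEN-01-301 and TEN-01-302. SAP Section 2.2.3 says "For each subject, the entire study will last for a total of approximately 52 to 55 weeks", counting the parent study.

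**The concern.** Pregnancy is an exclusion, but no procedure at Visit 1 tests for it. The only test result before dispensing is the one from the parent study. If Visit 1 takes place some time after that test, a woman who has conceived in between could satisfy criterion 3 and be given drug with an unrecognised pregnancy, and the site would have broken no written rule.

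What is at stake is avoidable fetal exposure. Section 9.8 requires pregnancies in subjects who have received study drug to be followed for congenital anomalies, so an exposure that a simple entry test could prevent is worth preventing. The group affected is narrow: women of child-bearing potential whose Visit 1 is later than their final parent-study visit.

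**Working it through.** **1. Is a gap planned?** Inputs: parent-study lengths of 16 weeks (TEN-01-301) and 26 weeks (TEN-01-302) from Section 5.2; treatment in this study of 39 and 26 weeks from the Protocol Summary; stated total of approximately 52 to 55 weeks.

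- From TEN-01-301: 16 + 39 = 55 weeks.
- From TEN-01-302: 26 + 26 = 52 weeks.

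The stated range is reproduced with a gap of 0 weeks.

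**2. Does anything else point to direct rollover?** Yes. Visit 1 has no vital signs, laboratory tests, ECG or physical examination. SAP Sections 3.7.2 to 3.7.4 take the enrolment values for these from the last parent-study assessments. Criterion 3 uses the last parent-study pregnancy test in the same way.

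**3. Does anything require it?** No. Section 4 and criterion 1 of Section 5.2 ask for completion only, Section 8 starts a separate clock at enrolment, and criterion 3 gives no maximum age for the test. The 52 to 55 week total is approximate. The Protocol Summary also words it as exposure to tenapanor, which time off drug between studies would not lengthen.

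**4. When is the first scheduled test in this study?** Visit 2 is at Week 13 ± 2:

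- earliest: (13 − 2) × 7 = 77 days
- latest: (13 + 2) × 7 = 105 days

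**5. How much drug is in hand by then?** Section 6.3 gives three bottles at Visit 1, Section 6.2 gives 66 tablets per bottle, and the dose is two tablets a day:

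- supply: 3 × 66 / 2 = 99 days
- possible dosing before the first test: min(77, 99) = 77 days to min(105, 99) = 99 days

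**6. Interval between the two tests.** With a rollover gap of g weeks, the parent-study test is g weeks old at dispensing, and the interval between tests is g + 11 to g + 15 weeks. The documents do not give g, so the values below are assumptions.

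| g (weeks) | Age of test at dispensing | Interval between tests |
|---|---|---|
| 0 (direct rollover) | 0 weeks | 11 to 15 weeks |
| 4 (illustration) | 4 weeks | 15 to 19 weeks |

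The 11 to 15 weeks after Visit 1 apply to every woman tested in this study, including one who conceives just after Visit 1. Only the g weeks before dispensing are at issue here.

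**The case against.** The strongest reply is that direct rollover is plainly the plan. The durations add up with no gap, the enrolment values come from the parent study, and no section describes a delayed Visit 1. On that reading the final parent-study test is the entry test. The parent protocols, which are not available here, may also make the final parent visit serve as Visit 1. This stands as evidence of intent, and it means that the frequency of a delayed Visit 1 cannot be established. It does not supply a rule: nothing in these documents stops a site from enrolling a woman weeks later on the old test.

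A second reply is that other safeguards exist: the pregnancy exclusion is reviewed at Visit 1, contraceptive use must be confirmed, and two telephone contacts that ask about adverse events come before Visit 2. These reduce the risk. But none of them is a test, and criterion 3 itself asks for a negative test in addition to contraception.

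A third reply is that the benefit is small, and that is fair. A urine test at Visit 1 finds only pregnancies already detectable that day. It will miss a very recent conception, and it does nothing about conception after Visit 1.

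A reader might infer that the planned design leaves women of child-bearing potential untested at entry. The documents do not support that. With same-day rollover, each has a negative test on the day of dispensing.

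**Conclusion.** The point holds conditionally and is minor. If Visit 1 is on the day of the final parent-study visit, there is no gap. If it is later, drug can be dispensed on a negative test of unlimited age plus a confirmation of contraception, with no scheduled pregnancy test for 77 to 105 days and up to 99 days of drug in hand.

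The conclusion rests on two things: that some women enrol after the final parent visit, which the documents neither plan nor forbid, and that the parent protocols do not close the gap, which cannot be checked here. The number of women dispensed drug while pregnant cannot be estimated from the documents. A reader might take the 77 to 105 days as the exposure that an entry test would save in general. It is not: the saving is confined to pregnancies already detectable at a delayed Visit 1. No safety summary or other analysis in the SAP is affected.

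**What to change.** In Protocol Sections 8.1 and 8.2.1.5, and in the Visit 1 column of the flow charts in Protocol Section 7 and SAP Section 2.2.3, add a urine pregnancy test for women of child-bearing potential. It should be read before dispensing, with a positive result confirmed by serum test as Section 8.2.1.5 already provides. Waive it when Visit 1 is on the same day as the negative final parent-study test. The eligibility criteria and the timing of Visit 2 can stay as they are.

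If the sponsor intends same-day rollover to be mandatory, one sentence saying so would close the gap instead.

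The cost is one urine test, of a kind already used at later visits, for women who do not roll over on the same day, and possibly a short delay in dispensing while a positive result is confirmed. Same-day rollover, which appears to be the plan, incurs no added cost.
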